12.2 Trial Design, Sample Size, and Study Duration

12.2.1 Trial Design: We will use a time to event continual reassessment method (TITE-CRM) trial design [11] to enroll a maximum of 30 patients onto this protocol.

The primary goal of this trial will be to determine the SBRT dose associated with a dose-limiting toxicity (DLT) in 20% of patients. DLT will be defined as grade ≥ 3 gastrointestinal toxicity (defined further below).

The TITE-CRM extends the original CRM by weighting each patient's contribution to the likelihood function described below. To determine the recommended dose for a newly enrolled patient, model parameters are estimated via the weighted likelihood. All previously enrolled patients who had either experienced toxicity or had completed the 12-month observation period without toxicity are assigned weights of 1; otherwise they are assigned weights equal to the proportion of the observation period they have completed.

The first patient in this study will enroll at dose level #2. Dose de-escalation can occur at anytime, though dose escalation will be restricted to 1 level between sequential patients. Additionally, before escalating the dose to the next level two conditions must be met: 1) the sum of the observation periods for all patients at the current dose level must be at least 12 months; and 2) at least one patient must have been under observation for at least 6 month at the current dose level. The rationale for these two conditions is mainly due to the short life expectancy of this patient population, which has a median survival of 8.25 months.

A two-parameter logistic regression model will be used to estimate the probability of toxicity at each dose level after each patient has been enrolled, which will inform the decision as to whether we should dose-escalate the patient in question. A final two-parameter logistic model will be fitted using follow-up data from 6 months after accrual of the last patient

Table 3. A priori toxicity estimation

Dose level	Probability of dose limiting toxicity
1	0.01
2	0.05
3	0.10
4	0.20
5	0.30

12.2.2 Dose Limiting Toxicity: The only toxicity observed thus far in pancreas SBRT has been related to nearby normal gastrointestinal organs, namely the duodenum and

stomach. Dose limiting toxicity in this study will be defined as any grade 3-5 gastrointestinal toxicity as measured by the Common Terminology for Adverse Events, version 4.0 (see appendix).

12.2.3 Maximum Sample Size: 30

12.2.4 Study duration: We anticipate accruing 12 patients per year, and will follow the last patient for a minimum of 6 months.

12.2.5 Interim analysis: This TITE-CRM trial design will de-escalate the radiation dose rapidly according to the observed dose-limiting toxicity. In addition to this built-in dose de-escalation we plan to conduct interim safety analysis after enrollment of every patient. We will stop the trial early if either of the following three conditions are met:

Condition 1 for early trial stoppage: more than 50% of patients at any dose level experience a dose-limiting toxicity.

Condition 2 for early trial stoppage: more than 34% of patients at dose level #1 experience a dose-limiting toxicity.

12.2.6 Operating Characteristics of the design: We used simulation to investigate the operating characteristics of our TITE-CRM configuration. We set the prior probability of toxicity at dose levels as in the table above, and investigate four different scenarios for the true underlying probabilities of toxicity:

- Scenario 1: Toxicity probabilities (.01, .05, .10, .20, .30) for dose 1-5, respectively (Prior Probability = True Probability)
- Scenario 2: Toxicity probabilities (.01, .05, .07, .10, .15) for dose 1-5, respectively (Prior Probability > True Probability)
- Scenario 3: Toxicity probabilities (.01, .05, .07, .10, .25) for dose 1-5, respectively (Prior Probability > True Probability)
- Scenario 4: Toxicity probabilities (.05, .10, .20, .30, .50) for dose 1-5, respectively (Prior Probability < True Probability)

We set our target rate of toxicity at the MTD to be .20, and set a vague normal prior with mean 0 and variance 1.34 (9). When a simulated patient enters the study, they are assigned to the dose chosen by the 'titecrm' function in the R library **dfcrm** (10), following the rules for dose escalation above. The incoming patient experiences a toxicity with probability given by the true underlying rate of toxicity for their assigned dose level, with toxicity time occurring uniformly between 0 and 12 months. Potential drop out (i.e. death) times are drawn randomly (with replacement) from the literature [5]. We set the number of simulations for each scenario at 5000.

Operating characteristics of the TITE-CRM simulation under different scenarios are included in the table below. 'Power' is defined as the simulated probability that the algorithm will recommend the correct MTD, defined in our simulation as the dose whose true toxicity probability is closest to, but not greater than, the target (dose 4, 5, 4, and 3 for each of the four scenarios, respectively) at the trials conclusion. Trial duration is the amount of time (in months) from the first patients' enrollment to the end of the final patients observation period. Total Obs. is the cumulative observation time (in months) on all 30 patients. Pr(Tox.) is the simulated probability of toxicity in that configuration, and Pr(Tox. Above MTD) is the simulated probability of a subject having toxicity at a dose above the MTD.

Table 4. Operating characteristics

[figure not shown]
	‘Power’	Trial Duration	Total Obs.	Time	Pr(Tox.)	Pr(Tox. Above MTD)
Scenario 1	0.341	39.4	237.0		0.091	0.016
Scenario 2	0.436	39.4	240.5		0.062	0.014
Scenario 3	0.369	39.5	239.1		0.071	0.022
Scenario 4	0.334	39.5	233.9		0.116	0.029

The probability of recommending each dose as the MTD by scenario is included in the table below.

[figure not shown]
Table 5. Probability of recommending each dose as the MTD

	Dose 1	Dose 2	Dose 3	Dose 4	Dose 5	MTD and (MTD - 1)
Scenario 1	0.000	0.123	0.386	0.341	0.150	0.727
Scenario 2	0.001	0.068	0.195	0.299	0.436	0.736
Scenario 3	0.003	0.069	0.204	0.369	0.356	0.573
Scenario 4	0.062	0.500	0.334	0.094	0.011	0.834

A boxplot of the number of patients treated above the MTD (treated above dose 4, 4, and 3, respectively) in scenarios 1, 3 and 4 is below.

A barplot of the average number of patients treated at each dose level with each scenario is below.

REFERENCES

1. Siegel R, Naishadham D Jemal A. Cancer statistics, 2013. *CA Cancer J Clin* 2013;63:11-30.

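### Section 12.2.1 plans a two-parameter logistic model with no prior on its parameters, 12.2.6 simulates with one scalar prior, and so Tables 4 and 5 are not shown to describe the planned rule

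*Combined protocol and SAP*

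**What the plan says.** Section 12.2.1 of the combined protocol and SAP describes the model used during the trial: "A two-parameter logistic regression model will be used to estimate the probability of toxicity at each dose level after each patient has been enrolled". On estimation it says that "model parameters are estimated via the weighted likelihood". For the end of the trial it adds: "A final two-parameter logistic model will be fitted using follow-up data from 6 months after accrual of the last patient". Table 3, in the same section, lists a priori DLT probabilities of 0.01, 0.05, 0.10, 0.20 and 0.30 for levels 1 to 5. These are point values, not a distribution for an intercept and a slope.

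Section 12.2.6 describes the simulations behind Tables 4 and 5: "We set the prior probability of toxicity at dose levels as in the table above". The target is 0.20, and the authors "set a vague normal prior with mean 0 and variance 1.34". Simulated patients follow the escalation rules of 12.2.1, and "they are assigned to the dose chosen by the 'titecrm' function in the R library" dfcrm. No curve form or other option is named.

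On timing, 12.2.4 "will follow the last patient for a minimum of 6 months", whereas 12.2.6 defines its reported duration as follows: "Trial duration is the amount of time (in months) from the first patients' enrollment to the end of the final patients observation period".

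**The concern.** The model in 12.2.1 informs every dose decision after the first patient and supports the primary aim. A logistic curve with intercept and slope has two unknowns, while the one scalar prior in 12.2.6 covers one. The two sections share the Table 3 probabilities, the target and the escalation rules. They do not agree on the number of parameters or on the parameter prior, and no text reconciles them. The citations attached to the prior and to the software lead, in the reference list, to two papers on fiducial placement, so the settings cannot be traced there.

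Two things are at stake. First, Tables 4 and 5 are the only evidence in the documents on how the design performs, and a reader cannot tell whether they apply to the rule that will be used. Second, a two-parameter model fitted by likelihood alone often has no finite estimate when DLTs are few, and 12.2.1 gives no rule for that case.

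**Working it through.** **1. The plan's own figures.** Inputs: Table 3 probabilities; target 0.20; 12-month linear weights; DLT time uniform over 0 to 12 months; 12 patients per year; start at level 2; both escalation conditions. The death times are not in the documents, so I assumed a Weibull with shape 1.2 and median 8.25 to 9.5 months. A one-parameter model with the N(0, 1.34) prior, choosing the highest level not above target, gives correct selection of 0.340 / 0.438 / 0.334 / 0.426 in Scenarios 1 to 4. Table 4 has 0.341 / 0.436 / 0.369 / 0.334. Simulated duration is 39.1 to 39.7 months across variants, against 39.4 to 39.5 stated. Scenarios 1 and 2 agree, Scenario 3 is 3.5 points off, and Scenario 4 is not matched by this variant (Monte Carlo standard error about 0.015 to 0.022). This is compatible with a one-parameter simulation but does not prove it. Full reproduction is not possible without the death times and the final selection rule.

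**2. When the literal two-parameter fit exists.** Take logit p = a + b × dose, with b free. A patient with a DLT adds log p; a patient without one adds log(1 − w·p), where w is the follow-up weight.
- No DLT: every term is largest as p goes to 0, for any w above 0, so the intercept runs off.
- All data at one level: only one probability is informed, so the slope is not identified.
- DLTs separated by dose: the likelihood keeps rising as the slope grows. With exactly one DLT, a finite fit needs non-DLT patients at both a lower and a higher level. With 6 patients per level, 0/6 and 1/6 at levels 2 and 3 sends the slope to plus infinity, 1/6 and 0/6 sends it to minus infinity, and 0/6, 1/6, 0/6 at levels 2 to 4 is finite.

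**3. Whether these states are expected.**
- At one patient per month, patient 1 reaches 6 months as patient 7 enters. Summed observation is then 6 + 5 + 4 + 3 + 2 + 1 = 21 months, above the required 12. Absent de-escalation, all data therefore sit at level 2 through patient 7's decision.
- The chance of at least one DLT on record by then, ignoring deaths, is 1 − ∏(1 − p·m/12) for m = 1 to 6. This is 0.085 at p = 0.05 (Scenarios 1 to 3) and 0.163 at p = 0.10 (Scenario 4).
- Table 4 implies 30 × 0.062 = 1.9 to 30 × 0.116 = 3.5 DLTs in the whole trial.
- In simulations under the assumptions of step 1, with patients dosed by the one-parameter model, I checked whether DLT and non-DLT patients overlap by dose. No finite two-parameter estimate exists in about 100% of trials at patient 8. In Scenario 1 the figure is about 90% at patient 15 and 68% at patient 20. At the final fit 6 months after last accrual it is about 30 / 45 / 45 / 19% in Scenarios 1 to 4, and roughly 18 to 45% across runs.

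**4. Data cut (secondary).** Entries fall at months 0 to 29, so the planned final fit is at 29 + 6 = 35 months. The simulated duration is 39.4 to 39.5 months, a gap of 4.4 to 4.5. At month 35, patients 25 to 30 can have at most 11, 10, 9, 8, 7 and 6 months, a shortfall of 1 + 2 + 3 + 4 + 5 + 6 = 21 patient-months before deaths are counted. Changing only the cut moved correct selection by about 1 to 2 points, within Monte Carlo error.

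**The case against.** The best defence is that 12.2.1 should not be read alone. Table 3 sits beside the two-parameter sentence, and 12.2.6 presents its settings as those of the trial's own design, so a reader may carry the N(0, 1.34) prior back into 12.2.1. On that reading the phrase two-parameter may be loose wording for a logistic curve with one constant fixed, and Tables 4 and 5 would be unaffected. This is a fair possibility, and it is one of the two outcomes allowed here. It still leaves 12.2.1 misdescribing the dosing model in two sentences. It does not supply a prior for a second parameter, and the failure to find a finite estimate applies only if no prior is used.

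It is also true that the escalation conditions bar escalation for patients 2 to 6 whatever the model says, so the early stakes are modest. The later decisions and the final fit do not have that protection. On the data cut, 12.2.4 sets a minimum and so permits longer follow-up, but 12.2.1 places the final fit at 6 months.

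A reader might go further and infer that the two models would pick different doses. Take 30 fully followed patients with DLTs in 0/6, 0/6 and 3/18 at levels 2 to 4. The one-parameter fit gives 0.128 to 0.134 at level 4 and 0.212 to 0.222 at level 5, depending on the curve; the unpenalised two-parameter limit gives 0.167 and 1.0. A nearest-to-0.20 rule separates them. The only MTD criterion in the documents, in 12.2.6, takes the dose nearest the target without exceeding it, and under that criterion both select level 4. The example therefore does not show a disagreement. With one assumed pair of priors, correct selection moved by 7 to 27 points, upward in three scenarios and downward in one. That depends on priors the plan does not state and is illustrative only.

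A reader might also infer that Tables 4 and 5 are wrong, or that patients would be harmed in a particular direction. The documents support neither.

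**Conclusion.** The point holds in this form: the number of parameters and the parameter prior differ between 12.2.1 and 12.2.6 and are not reconciled. Either the planned model is not the simulated one, or 12.2.1 misdescribes it, so the stated correct-MTD probabilities of 0.334 to 0.436 are not shown to describe the planned rule. Read literally, the rule in 12.2.1 fails in data the trial should expect: nearly always at patient 8, and in roughly one trial in five to almost one in two at the final fit.

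That the simulation used one parameter is inferred from the single prior. The failure rates rest on assumed death times, accrual of one patient per month and dosing by the one-parameter model. The difference in data cut is real, but its effect on selection appears small. No frequency of different dose choices is claimed, and nothing is said about which level is right.

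**What to change.** State one working model for the dose decisions, the final MTD and the simulations. The simplest edit is to replace both two-parameter sentences in 12.2.1 with the model actually coded for Tables 4 and 5. Name the curve form, any fixed constant, the prior, the point estimate and the dose-selection rule. If two parameters are kept, give priors for both and a positive-slope constraint, then rerun and restate Tables 4 and 5.

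Align the final data cut in the same edit, and rerun the tables if the retained cut differs from the code. Correct the two citations for the prior and the software.

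The cost is wording, plus a rerun of existing simulations if the retained model or cut is not the one coded. Sample size and visits do not change. Adopting the simulated cut would move the final fit back by about 4.4 to 4.5 months.

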11.0 DATA COLLECTION

11.1 Data and Safety Monitoring Plan

In addition to adverse event monitoring and clinical oversight by the principal investigator and co-investigators, quality assurance of the study will be performed by the clinical trials office internal monitor. Monitoring intervals will be dependent upon the number of patients enrolled.

This study will also use the UCSD Moores Cancer Center Data Safety and Monitoring Board to provide oversight in the event that this treatment approach leads to unforeseen toxicities. The DSMB will review data from this study semi-annually.

Data from this study will be reported semi-annually and will include:

- 1) the protocol title, IRB protocol number, and the activation date of the study.
- 2) the number of patients enrolled to date
- 3) the date of first and most recent patient enrollment
- 4) a summary of all adverse events regardless of grade and attribution
- 5) a response evaluation for evaluable patients
- 6) a summary of any recent literature that may affect the ethics of the study.

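### Unless the unlisted third stopping condition covers it, nothing in the plan pauses enrolment or requires a DSMB decision after an SBRT-related death

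*Combined protocol and SAP*

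**What the plan says.** Section 12.2.5 introduces its rules with "We will stop the trial early if either of the following three conditions are met" and then gives only two. The first is "Condition 1 for early trial stoppage: more than 50% of patients at any dose level experience a dose-limiting toxicity". The second is a DLT share above 34% at level 1. The same section says "we plan to conduct interim safety analysis after enrollment of every patient".

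Section 12.2.2 sets the event: "Dose limiting toxicity in this study will be defined as any grade 3-5 gastrointestinal toxicity". Section 12.2.1 sets its weight in the dose model: "All previously enrolled patients who had either experienced toxicity or had completed the 12-month observation period without toxicity are assigned weights of 1". Neither the event definition nor the weight separates grade 5 from grade 3.

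In section 10.4 the principal investigator hears of every SAE within 24 hours. The HRPP and the DSMB are told within 10 business days of an unanticipated problem. Section 11.1 gives the DSMB its role, "to provide oversight in the event that this treatment approach leads to unforeseen toxicities", and its timetable: "The DSMB will review data from this study semi-annually".

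**The concern.** A treatment-related death in a dose-escalation trial normally calls for an independent look before anyone else is exposed. Here the two listed rules see only a proportion, so one fatal perforation among several patients at a level can leave both unmet. The TITE-CRM was chosen so that accrual need not wait for late toxicity (12.1.1). That makes an event-triggered pause the natural complement to the model, and none is written. At stake is whether the next patient can start SBRT, perhaps at the same dose, before an independent body has decided that the trial should go on.

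**Working it through.** The plan gives no figure of its own on this point, so there is none to reproduce. The check has four parts.

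**1. What each safeguard does after a related death**

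| Provision | Trigger | Consequence stated |
|---|---|---|
| Conditions 1 and 2 (12.2.5) | DLT proportion | Trial stops |
| Safety analysis (12.2.5) | Each enrolment | None beyond the listed conditions; no decision-maker named |
| Dose model (12.2.1) | Each new patient | Dose recommendation |
| SAE notice (10.4) | Any SAE | Investigator told within 24 hours |
| Unanticipated-problem notice (10.4) | For a serious event, the investigator's opinion that it was unanticipated and possibly related | DSMB and HRPP told within 10 business days |
| DSMB review (11.1) | Calendar, every 6 months | Review |
| Sections 10.5 and 10.6 | Individual patient | That patient is removed |

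Step 5 of section 10.3 sends the reader to 10.6 for protocol-specific expedited rules, but 10.6 covers only removal from study. No row pauses enrolment or requires an independent decision.

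**2. When one fatal GI DLT meets a listed condition**

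Condition 1 needs the smallest d with d/n > 0.50: 1 of 1, 2 of 2, 2 of 3, 3 of 4, 3 of 5, 4 of 6. Condition 2 (level 1) needs d/n > 0.34: 1 of 1, 1 of 2, 2 of 3 (1/3 = 0.333 is not enough). So a single fatal DLT stops the trial only as 1 of 1 at its level, or as 1 of 2 at level 1.

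**3. What the dose model does next**

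Inputs: Table 3 skeleton, target 0.20, normal prior with mean 0 and variance 1.34 (12.2.6). The weighted likelihood is the product of (w·p)^y · (1 − w·p)^(1 − y). The parameter b is set at its posterior mean, and the level with estimated risk nearest 0.20 is recommended. Two one-parameter models were run: power, p = s^exp(b), and logistic with intercept 3. This is an assumption: 12.2.1 names a two-parameter logistic, but 12.2.6 gives a single prior.

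Typical weights come from Table 4, where "Total Obs. is the cumulative observation time (in months) on all 30 patients". Dividing by 30 × 12 = 360 gives 237.0/360 = 0.658, 240.5/360 = 0.668, 239.1/360 = 0.664 and 233.9/360 = 0.650. Level-2 weights of 0.65 to 0.67 are therefore used below.

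| Case (1 DLT, weight 1) | Risk at that level, power | Risk at that level, logistic | Next dose |
|---|---|---|---|
| A. 6 DLT-free at level 2; 1 of 6 at level 3, other five at weight 0.5 | 0.172–0.175 | 0.180–0.185 | Level 3 in both |
| B. As A, other five at 5, 4, 3, 2 and 1 months (mean weight 0.25) | 0.207–0.211 | 0.239–0.248 | Level 3, except level 2 in the logistic model at level-2 weight 0.65 |
| C. 1 of 6 at level 4, others fully observed | 0.187 | 0.172 | Level 4 in both |
| D. 1 of 3 at level 2, others at weight 0.5 | 0.383 | 0.712 | Level 1 in both |

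Case B is monthly accrual (12 per year, 12.2.4) with the first level-3 patient's DLT at month 6, the median time in 12.1.1. Case D gives level 1 for 1 of 4, 5 or 6 as well. It depends on the half weights: with the others fully observed, the power model stays at level 2 after 1 of 4 (estimate 0.218).

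**4. Exposure at 12 patients per year**

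- Notice window: 10 business days = 14 calendar days; 14/365.25 × 12 = 0.46 patient.
- Interval between DSMB reviews: 6 months = 6 patients.

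**The case against.** The strongest reply is that the rule set is visibly incomplete: the unlisted third condition might be a death rule, so the gap cannot be asserted outright. That stands, and the point is made conditional on it.

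The second reply is that the safeguards already work. A fatal GI event is a DLT. The DLT appendix also covers hepatic failure, biliary events and intra-abdominal and retroperitoneal hemorrhage. Deaths are named in the first item of the unanticipated-problem definition. The DSMB may well act on a notice under procedures outside these documents. Most of this stands too. Section 6.2 describes GI injury only as far as surgery or hospitalization, so a related death would probably be judged unanticipated and reach the DSMB. The gap for non-GI deaths is narrow: kidney failure, for example, is listed as rare and has a dose constraint. What remains is that these are notices, reviews and dose estimates, with no pause and no deadline for a decision.

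Three stronger readings are tempting:

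- **About 6 patients would be treated before any independent review.** That needs the death to be judged anticipated, the less likely case.
- **The model would simply repeat the dose.** Cases A to D show that this depends on level and follow-up. Where the estimate is below 0.20, the model is doing its job on the DLT rate.
- **Fatal events are to be expected in some number.** The documents give no such figure.

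A last reply is that the pause could be costly: tumor progression itself causes bleeding and obstruction (1.1), stage IV patients are eligible, and the trigger includes possibly related deaths. This stands unless someone independent confirms the progression exclusion and the review is time-limited.

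**Conclusion.** The point holds, as a modest patient-safety improvement. Subject to the unlisted condition, the documents contain no pause and no required DSMB decision after an SBRT-related death, and one such death will usually leave both listed conditions unmet. The likely exposure before the DSMB is notified is about half a patient, and no time limit for a decision follows that notice. A repeat of the same dose is a plausible next step at level 3 or 4, but not at level 2 while follow-up is immature.

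The absence of the rule rests on the text alone. The dose results rest on one-parameter models and assumed follow-up weights. The exposure figure rests on accrual of 12 per year and on the death being judged unanticipated. It would be wrong to infer that the plan leaves deaths unmonitored.

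**What to change.** Add to 12.2.5 and mirror in 11.1:

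*Any grade 5 event judged possibly, probably or definitely related to SBRT, GI or not and anticipated or not, suspends new enrolment and any SBRT course not yet begun. The suspension lasts until the DSMB has met ad hoc and recommended whether and how to continue, within a stated limit (for example 2 weeks). An exclusion for documented tumor progression must be confirmed by the DSMB or its chair, not by the investigator alone.*

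Separately, state the third stopping condition or change the count to two. The DLT definition and dose model stay as they are.

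The change uses the existing DSMB and the 10.3 attribution categories. Each 2-week pause delays about 0.46 enrolment and any patient waiting for SBRT. The number of pauses is unknown; for 1 to 5 (assumption), the total is 2 to 10 weeks against about 130 weeks of accrual (30/12 = 2.5 years), or 1.5% to 7.7%. With an 8-week review, five pauses would take 40 weeks (31%), which is why the limit matters.

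### The early-stopping rule has no minimum number or stated denominator and lists two of its three announced conditions; Tables 4 and 5 appear to exclude stopping, and one Table 4 cell must be 0.

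*Combined protocol and SAP*

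**What the plan says.** Section 12.2.5 adds a trial-level safety stop to the dose-finding model: "In addition to this built-in dose de-escalation we plan to conduct interim safety analysis after enrollment of every patient". The stop is introduced with "We will stop the trial early if either of the following three conditions are met". Two conditions follow, and the text then goes straight to Section 12.2.6:

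- Condition 1: "more than 50% of patients at any dose level experience a dose-limiting toxicity".
- Condition 2: "more than 34% of patients at dose level #1 experience a dose-limiting toxicity".

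Section 12.2.5 does not say which patients form the denominator or how many must be at a level before the percentage applies. It also does not say how to count patients still inside the 12-month window or patients who died without a DLT.

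Section 12.2.1 does define partial counting, but for the dose model. Patients with incomplete follow-up are "assigned weights equal to the proportion of the observation period they have completed".

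Section 12.2.6 says that simulated patients were assigned doses under the escalation rules; it does not mention the stopping conditions. It names doses 4, 5, 4 and 3 as the correct MTD in Scenarios 1 to 4. It defines the last column of Table 4 as the probability of toxicity at a dose above the MTD. For Scenario 2 that column shows 0.014.

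**The concern.** The primary endpoint is toxicity, so the rule that ends the trial for toxicity should be executable as written and reflected in the reported operating characteristics. There are three problems.

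- A percentage checked after every enrolment with no minimum can be exceeded by one event in one patient. Followed literally, that ends the trial at all levels, although the model has its own de-escalation for such an event.
- A reader of Tables 4 and 5 will take them as the properties of the planned trial. If stopping was left out, they describe a different procedure.
- One safety cell in Table 4 contradicts the section's own definition, which puts the cut-off used for that column in doubt.

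The mismatch between three announced and two listed conditions is smaller. It may be a slip for two (the word before it, either, fits two) or a lost line, and the document does not show which.

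**Working it through.** **1. Smallest numbers that trigger a stop, counting all enrolled patients at the level**

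| DLTs / patients | Percentage | Condition 1 (>50%, any level) | Condition 2 (>34%, level 1) |
|---|---|---|---|
| 1/1 | 100% | stop | stop |
| 1/2 | 50% | continue | stop |
| 1/3 | 33.3% | continue | continue |

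The check follows an enrolment, so it also matters whether the new patient counts. If the only patient at a level has a DLT and the next patient joins that level, the fraction is 1/2 when the new patient counts and 1/1 when not. If the next patient goes to another level, it is 1/1. Section 12.2.5 does not settle this.

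**2. How often the rule would stop the trial (illustrative)**

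Inputs from the document: Table 3 probabilities, target 0.20, prior variance 1.34, start at level 2, both escalation conditions, 30 patients, 12 per year, DLT times uniform over 12 months, and the four true-rate scenarios.

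Assumptions not in the document: death times exponential or Weibull (shape 1-2) with median 8.25-11.8 months; monthly or Poisson entry; one- or two-parameter model with assumed details; new patient counted or not. Fourteen settings were run, with 1,000 or 2,000 trials per scenario (Monte Carlo standard error up to 1.6 points).

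| All enrolled, no minimum | Sc. 1 | Sc. 2 | Sc. 3 | Sc. 4 |
|---|---|---|---|---|
| Trials stopped, 14 settings | 4-9% | 2-4% | 2-6% | 7-18% |
| Separate run (one-parameter model, exponential deaths, median 8.25 months, 1,500 trials) | 4.3% | 1.9% | 2.3% | 9.4% |

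Across the 14 settings, stops on a level holding one patient occur in about 1-7% of trials. These rates are not calibrated to the plan. Without stopping, the separate simulator gave Scenario 2 power of 0.62-0.68, against 0.436 in Table 4.

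**3. Do Tables 4 and 5 include stopping?**

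Table 5 row sums:

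- Scenario 1: 0.000 + 0.123 + 0.386 + 0.341 + 0.150 = 1.000
- Scenario 2: 0.001 + 0.068 + 0.195 + 0.299 + 0.436 = 0.999
- Scenario 3: 0.003 + 0.069 + 0.204 + 0.369 + 0.356 = 1.001
- Scenario 4: 0.062 + 0.500 + 0.334 + 0.094 + 0.011 = 1.001

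Power in Table 4 equals the MTD entry in Table 5 in all four scenarios. So every simulated trial ends with a recommended dose, and no share is set aside for stopped trials. Total observation time is defined on all 30 patients, and durations are 39.4-39.5 months throughout. This points to no stopping. It is not proof: a stopped trial could still have been given a recommendation, and a rarely triggered rule would leave little trace in mean duration.

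**4. The Scenario 2 cell**

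True rates are 0.01, 0.05, 0.07, 0.10 and 0.15, all below 0.20. The MTD is therefore dose 5, as the section states. No dose lies above dose 5, so the probability is 0 by definition, whatever the simulation settings. Table 4 gives 0.014.

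A likely source is toxicity at dose 5. Dividing by the true dose-5 rate gives 0.014/0.15 = 9.3% of patients in Scenario 2 and 0.022/0.25 = 8.8% in Scenario 3. The two scenarios share the same rates at doses 1 to 4, so similar use of dose 5 is expected. This is inference. If dose-5 toxicity was counted throughout, Scenarios 1 and 3 are unaffected (MTD dose 4), but Scenario 4 (MTD dose 3) would omit toxicity at dose 4.

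**The case against.** Counting patients at a dose level naturally means everyone enrolled there, so the denominator is less open than it looks: partly observed patients and deaths without a DLT are simply included. The 34% limit lies just above one in three, which suggests that small counts were considered. The data and safety monitoring board reviews the trial twice a year (Section 11.1) and could use judgement. The tables most naturally describe the algorithm alone, and one sentence would say so. The Scenario 2 cell feeds no stated decision, and the boxplot of patients treated above the MTD correctly leaves that scenario out.

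Most of this stands and limits the size of the point. It does not supply a minimum number, reconcile the count of conditions or make 0.014 possible. The cell could be non-zero if the MTD meant each trial's recommended dose, but the section defines it by the true rates; that alternative gave about 0.007 in simulation.

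A reader might infer something stronger: that the Section 12.2.1 weights apply to the stopping rule. Five patients then enter a level at months 0 to 4, the first has a DLT before the month-4 check, and the fraction is 1/(1 + (3+2+1+0)/12) = 67% instead of 1/5 = 20%. Simulated stopping under that reading was roughly 25-76%. The documents do not support this as the headline. Section 12.2.1 confines the weights to the likelihood used for dose assignment, and Section 12.2.5 counts patients. The example also depends on monthly entry: with two-month gaps it is 1/(1 + (6+4+2+0)/12) = 50%, which does not exceed the limit. The text does not exclude the weights either, which is the reason to state the denominator.

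**Conclusion.** Wrong as written, at modest size. Three points need only the text: three conditions are announced and two listed; with no minimum, 1/1 at any level or 1/2 at level 1 literally ends the trial; and the Scenario 2 value of 0.014 must be 0. That Tables 4 and 5 exclude stopping is the most natural reading of Section 12.2.6, not a certainty.

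On the all-enrolled reading, stopping occurs in about 2-18% of trials. This range rests on assumed death times and model details and was not matched to Table 5, so it shows an order of magnitude only. Other denominators that the text does not exclude would stop more often, but this is secondary and their rates are equally illustrative. The documents do not support a conclusion that the trial as planned would stop in a quarter or more of cases.

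**What to change.** - Section 12.2.5: reconcile the number of conditions, by adding the missing one or changing the count.
- Section 12.2.5: state the denominator for each percentage, including partly observed patients, patients dead without a DLT and the patient just enrolled, and whether a minimum number applies. This review proposes no threshold.
- Section 12.2.6: re-run Tables 4 and 5 with the stopping rules as adopted, or state that they exclude them.
- Table 4: correct the Scenario 2 entry for toxicity above the MTD to 0 or not applicable, and check the cut-off used in that column, Scenario 4 in particular.

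The cost is some protocol wording, one table cell, and either one re-run of existing simulation code or one sentence of disclosure. The downside is that the restated operating characteristics may look slightly less favourable.
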